5.5.5 Permitted dose adjustments of study treatment

This section describes the actions that are required if a systolic BP decrease (i.e. <5th percentile for age) occurs during the administration of study drug and is confirmed by two measurements taken 10 minutes apart (in patients with intermittent BP measurements) or by a consistent measurement over ≥ 5 min (in patients with invasive continuous BP measurements). This event is considered a “systolic blood pressure decrease event” (SBPDE) and must be recorded as such on the appropriate eCRF.

If the SBP falls to <5th percentile for the age of the patient ([AHA PALS guidelines 2010, Kleinman 2010](#), see [Appendix 4](#)) and is a confirmed SBPDE per the criteria in the previous paragraph, then the following steps are required:

1) In all patients:

Assess the patient and treat alternative causes of hypotension (consider hypovolemia, arrhythmia, heart-lung interactions, concomitant medications, pneumothorax or pericardial tamponade, hardware malfunction or measuring error etc.)

2) As clinically indicated, the following steps should be taken, preferentially in the indicated order (however, the options can be applied in sequence or separately at the investigator's discretion):

1. Increase the infusion rate of inotropic and/or vasoactive drugs as clinically indicated up to a vasoactive score of 20 and/or
2. Reduce the serelaxin infusion rate by 50% and/or
3. Discontinue serelaxin infusion

Patients who tolerate the reduced serelaxin infusion rate should remain on this reduced infusion rate for the remainder of the 48 hour infusion period, as tolerated. The exact time and date of the reduction of the study drug infusion rate must be recorded on the Drug Administration Record case report form. All assessments, including PK sampling, should continue per protocol even if the dose rate is reduced. Time from initiation of study drug infusion to completion must not exceed a total of 48 hours.

Dosing may be discontinued at any time at the discretion of the investigator. Reasons for which the investigator may discontinue the study drug include, but are not limited to, serious or intolerable AEs suspected to be causally related to study drug. In the event that study drug

administration is discontinued, regardless of the reason, the patient will continue to be followed at all study visits defined in the protocol. PK sampling should follow the schedule that is planned for after completion of the study drug (see [Section 6.6.2](#)). The exact time and date of study drug discontinuation must be recorded.

Re-administration of study drug, once terminated, is not allowed.

Changes in study drug dose must be recorded on the Dosage Administration Record CRF.

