6.5.2 Vital signs, respiratory parameters and clinical assessments

Vital signs, respiratory parameters and clinical assessments will be performed at multiple time points as described below. These measurements may be made and recorded by trained healthcare personnel as part of their routine clinical duties, as well as by study personnel.

Vital signs, respiratory parameters and clinical assessments to be evaluated:

- HR, SBP, Mean Arterial Pressure (derived), DBP
- RR (respiratory rate of the patient)
- SpO₂ (pulse oximeter)
- Hourly per kg urine output
- ETCO₂ (end-tidal (expiratory) CO₂) or TcCO₂ (transcutaneous CO₂), if available
- CVP (central venous pressure) and LAP (left atrial pressure), if available
- PAP (pulmonary artery pressure – systolic and diastolic), if available
- Ventilation parameters (where available – for spontaneously breathing patients only FiO₂ [according to the table in [Appendix 7](#)] should be recorded):
 - o Mode of ventilation: invasive, non-invasive mechanical ventilation or spontaneous breathing
 - o FiO₂ (Oxygen fraction in the inspired gas) [according to the table in [Appendix 7](#)] should be recorded in addition to the ventilator parameters (PIP, PEEP, MAP, V_T) specified in [Section 6.4.2](#)

- Oxygenation index ($\text{FiO}_2 \times \text{MAP}$)/ PaO_2 (for patients on mechanical ventilation only) and $\text{PaO}_2/\text{FiO}_2$ ratio, will be calculated
- Co-medication and dose (including [dose – per min or hour] or [infusion rate + concentration] for continuous infusions, e.g. inotropes, vasoactive drugs, sedation and analgesia)
- Discontinued co-medications during the interval (all medications)
- Non-medical therapies in the interval (including but not limited to the following: physiotherapy, ergotherapy, endotracheal suctioning or repositioning, mobilization, transportation)

Vital signs, respiratory parameters (including the ventilator parameters PIP, PEEP, MAP, V_T specified in [Section 6.4.2](#)) and clinical assessments must be closely monitored during the infusion of the study drug. The time points to be collected in the eCRF for the evaluation of vital signs, respiratory parameters and clinical assessments (hourly time points are approximate) are as follows:

- Baseline
- Every 2 hours for 4 hours at the start of each of the three dose levels
- Every 4 hours for the remainder of each infusion period
- Every 4 hours during the 24 hours post discontinuation or completion of study drug infusion

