9.5.2 Safety variables

Adverse events, SAEs and Death

Adverse events (AEs, SAEs and AEs leading to discontinuation) will be summarized by cohort and dose group and for all subjects in the SAF for the entire study period, during each of the 16 hour dose escalation periods and over the post infusion period. Adverse events (number and percent) will be presented by system organ class and MedDRA preferred term.

In addition, a summary of AEs by preferred term and severity, using the worst reported severity grade for each event for the subject, will be provided. The number and percentage of patients with AEs possibly related to study medication will be summarized by age cohort and dose group and for all patients as well. These summaries will be presented for the entire study period, during each of the 16 hour dose escalation periods and over the post infusion period, respectively.

Death (if any) will be summarized by system organ class and MedDRA preferred term as well. AEs, SAEs and death will be also presented in data listings at individual patient level.

Laboratory, vital signs, body weight and decreased blood pressure events

Laboratory data will be summarized by presenting shift tables using extended normal ranges (baseline to most extreme post-baseline value), summary statistics of raw data and change

[REDACTED]

[REDACTED]

from baseline (mean, confidence interval, median, standard deviation, 1st and 3rd quartiles Q1 and Q3) at each assessment time point by age cohort and dose group and for all subjects. Notably abnormal values for individual subjects will be flagged in data listings.

Vital sign data and clinical assessments (including HR, SBP and DBP, ventilation parameters etc. as described in [Section 6.5.2](#) excluding the efficacy variables specified in [Section 6.4.1](#)) will be descriptively summarized as appropriate by presenting absolute values and change from baseline at each assessment time point for each age cohort and dose group and for all patients. In addition, respiratory parameters including FiO₂, and oxygenation index (FiO₂×MAP)/PaO₂ (for patients on mechanical ventilation only), and PaO₂/FiO₂ ratio, will also be summarized by presenting absolute values and change from baseline at each assessment time point by age cohort, dose group and ventilation mode.

The absolute values and change from baseline at each visit in body weight will be summarized descriptively by age cohort and dose group and for all patients.

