5.4 Medical History

Medical history entered on the medical history CRF page at screening [REDACTED] will be coded using the MedDRA dictionary. Medical history and protocol solicited events (only for post-surgical patients) will be listed at the individual patient level for the SAF.

6 Study medication

Data entered on the Dosage Administration Record CRF page will be listed at the individual patient level for the SAF. This will include dose prescribed (ug/kg/day), start/end date and time of the infusion, concentration (ug/ml), rate of infusion (mL/h) and reason for the dosage administered.

7 Concomitant medication

Prior and concomitant medications, continuous intravenous concomitant medications, surgical and medical procedures and use of mechanical ventilator will be listed at the individual patient level for the SAF. The medication name will be coded using therapeutic class (ATC code) and preferred term (PT).

8 Pharmacokinetic (PK) data

PK concentration data will be listed at the individual patient level for the SAF. Invalid PK concentration data will be noted. A graphical presentation will be employed to show individual serelaxin concentration-time (actual) profiles by age cohort within each dose group. These figures will be prepared for the PK analysis set.

9 Selected vital signs for safety (SBP, DBP, HR and RR)

Summary statistics (n, mean, standard deviation, median, Q1, Q3, minimum, and maximum) will be provided by age cohort within each dose group for the measurement at each visit and change from baseline values for the following parameters for the safety population:

- Systolic blood pressure (SBP)
- Diastolic blood pressure (DBP)
- Heart rate (HR)
- Respiratory rate (RR)

10 Adverse Events (AEs), SAEs and Deaths

A treatment emergent adverse event is defined as an adverse event that occurs at or after the start of the study treatment. Treatment emergent adverse events including non-serious AEs, SAEs, AEs (including non-serious AEs and SAEs) and AEs leading to discontinuation will be

summarized descriptively (using number and percentage) by age cohort within each treatment group and in the overall group. Similarly, deaths will be summarized descriptively as appropriate. The number and percentage of these events will be presented by system organ class (SOC) and MedDRA preferred term (PT). All AEs will be listed at the individual patient level. These analyses will be performed for the SAF.

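### The SBP and DBP tables leave out concurrent vasoactive and inotropic support, so they confound serelaxin with changes in that support; the net direction is unknown

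*Protocol*

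**What the plan says.** **Entry and later changes.** Inclusion criterion 3 requires a stable dose of vasoactive and/or inotropic agents. Protocol Section 3.1 defines stable as two hours without a change above 20% in infusion rate. In the readable text nothing holds the dose fixed afterwards. Protocol Sections 5.5.7 and 5.5.8 let the investigator add, modify or stop other therapy as the patient needs.

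**Response to hypotension.** For a confirmed SBPDE, Protocol Section 5.5.5 starts, in all patients, with "Assess the patient and treat alternative causes of hypotension". Step 2 gives three options in a preferred order: "Increase the infusion rate of inotropic and/or vasoactive drugs as clinically indicated up to a vasoactive score of 20", then halving the serelaxin rate, then stopping it. It adds that "the options can be applied in sequence or separately".

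**Data collected.** Protocol Section 6.5.2 puts co-medication dose in the same assessment set, at the same time points, as SBP and DBP, including doses "for continuous infusions, e.g. inotropes, vasoactive drugs, sedation and analgesia". Exclusion criterion 11 already defines a vasoactive score that combines these drugs.

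**Planned outputs.** Under Protocol Section 9.5.2, vital signs "will be descriptively summarized as appropriate by presenting absolute values and change from baseline at each assessment time point". Under SAP Section 9, summary statistics for SBP and DBP "will be provided by age cohort within each dose group for the measurement at each visit and change from baseline values". Neither adds a support covariate, stratum, flag or parallel display. In SAP Section 7, "continuous intravenous concomitant medications, surgical and medical procedures and use of mechanical ventilator will be listed at the individual patient level". Protocol Section 9.5.2 also promised the number and proportion of patients with a confirmed SBPDE by dose level, dose group and age cohort. SAP Section 11 reduces this to a listing that depends on data availability. The readable list of summary tables in SAP Section 1 has no vasoactive summary, and SAP Addendum 1 Section 2.2 adds neither blood pressure nor vasoactive support.

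**The concern.** Safety is a primary objective, and arterial pressure is the first-named secondary haemodynamic parameter. Hypotension is the recognised concern from the adult trials (Protocol Section 3.6). The protocol itself names a co-intervention that acts directly on this outcome. The SAP then tabulates the outcome without the co-intervention.

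A pressure held up by a higher infusion rate enters the table as little or no change. A pressure that fell because support was weaned enters as a fall under serelaxin. A reader of the summary cannot tell these apart. With the SBPDE counts gone, the SBP and DBP tables are, apart from the adverse event tables, the only aggregate blood pressure safety output in the SAP.

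**Working it through.** The documents give no effect size, standard deviation or precision figure for blood pressure, so there is no stated figure to reproduce. Two checks apply.

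**1. How far one supported patient can move a cell mean**

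Inputs:
- Entry threshold: 25th percentile SBP by age and sex (inclusion criterion 4, Appendix 3).
- SBPDE trigger: below the 5th percentile SBP by age (Section 5.5.5, Appendix 4).
- Planned cell sizes (Section 3.1): 3 in every low-dose cell; 6 in the high-dose cells of cohorts 3 and 4; 3, at most 6, in the high-dose cells of cohorts 1 and 2.

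Gap = Appendix 3 value − Appendix 4 value. Shift in cell mean = gap / n, if one patient at the trigger is brought back to the entry threshold by support alone.

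| Age cohort | Gap (mmHg) | Shift, n = 3 | Shift, n = 6 |
|---|---|---|---|
| 1 (6 to <18 years) | 5 to 22 | 1.7 to 7.3 | 0.8 to 3.7 |
| 2 (1 to <6 years) | 6 to 8 | 2.0 to 2.7 | 1.0 to 1.3 |
| 3 (1 month to <1 year) | 75 − 70 = 5 | 1.7 | 0.8 |
| 4 (birth to <1 month) | 70 − 60 = 10 | 3.3 | 1.7 |

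In cohort 1 the smallest gap is, for example, 95 − 90 = 5 at age 10, and the largest is 112 − 90 = 22 in boys aged 17. Then 5/3 = 1.7, 22/3 = 7.3, 5/6 = 0.8 and 22/6 = 3.7. The appendices cover systolic pressure only, so this gives no size for DBP.

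**2. Which way the mean moves**

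Let d be the change due to serelaxin, e the pressure change from altering support, r the share of patients with support raised and w the share with it lowered. Then

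observed mean change = d + e × (r − w).

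The documents give none of these four quantities. For illustration only, assume d = −8 mmHg and e = 5 to 10 mmHg:

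- r = 1/3, w = 0: −8 + 1.7 = −6.3, to −8 + 3.3 = −4.7 (understated).
- r = 0, w = 1/3: −8 − 1.7 = −9.7, to −8 − 3.3 = −11.3 (overstated).
- r = w: −8.0 (no net bias).

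The sign follows r − w. The formula also takes every increase to be pressor, which need not hold: Protocol Section 1.1 names the inodilators milrinone and dobutamine among background drugs.

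**The case against.** **Support is part of standard care.** The objectives concern serelaxin given on top of standard care, and pressure observed under adjusted care describes exactly that. No blood pressure hypothesis is tested. This is fair: the tables are valid as a description. But Section 2.2 asks for the haemodynamic effects of different serelaxin doses, and a table silent on support cannot separate those from changes in other infusions.

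**The information is in the listings.** A reader might infer that rescue hides hypotension. The documents do not support that for a confirmed event: an SBPDE is confirmed before the response to it and has its own record. SBPDEs, the vital signs around them and continuous infusions are all listed by patient, and interim reviews cover hypotension events. With 3 to 6 patients per cell, listings are usable. They do not cover everything: support raised before the 5th-percentile trigger is met creates no SBPDE, and the reader must match several drugs to pressure by hand.

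**Stronger readings that fail.**
- A reader might conclude that the tables understate serelaxin's effect. Support may also be reduced, some agents are inodilators, serelaxin itself may be halved or stopped, and there is no control arm, so the overall direction is not established.
- A reader might take raising support to be the first response to hypotension. It is the preferred first option of step 2, after assessment of alternative causes, and the options may be used separately.
- A reader might expect the distortion to be largest at the top dose. Protocol Section 3.6 reports adult hypotension events without a dose-response, and Section 5.5.4 bars escalation when a requirement for dose adjustment is met.

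**Context and redaction.** The SAP serves an abbreviated report after early termination. Protocol Section 6.4.2 and parts of Section 9.5.1 and SAP Section 11 are redacted, so a vasoactive analysis there cannot be excluded. SAP Section 9 and the table list in SAP Section 1 are readable and contain none.

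**Conclusion.** The point holds as confounding of unknown net direction. The SBP and DBP means combine serelaxin with changes in support, and they are biased toward no effect in patients whose support was raised for hypotension. One such patient can move a cell mean of SBP by about 1.7 to 7.3 mmHg with 3 patients, or 0.8 to 3.7 mmHg with 6. This assumes a patient at the SBPDE trigger is returned to the entry threshold by support alone. A patient may start above that threshold, and recovery may be smaller or larger than the gap. How many patients had support raised or lowered is not given, so no overall bias can be stated. The listings soften the problem but do not remove it.

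**What to change.** In SAP Section 9:

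- Derive the exclusion-criterion-11 vasoactive score at baseline and at each SBP/DBP time point from the infusion doses already collected under Protocol Section 6.5.2. Show the score and its change from baseline beside SBP and DBP.
- Flag blood pressure readings taken after a change in support in either direction. Include vasodilators such as nitroprusside, which Protocol Section 1.1 names as standard care but the score omits.
- Restore the Protocol Section 9.5.2 count of patients with a confirmed SBPDE by dose level. Beside it, as a separate count, show patients with a rise in score.
- Label the display descriptive and post hoc. Addendum 1 already added analyses after database lock, so the route exists.

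Restricting the tables to readings before the first rise in support is not advised: it selects on the outcome and could nearly empty a cell of 3.

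The cost is one derived variable and one or two tables, with no new data and no error-rate consequence. The drawback is that score changes are not specific to serelaxin, and a rise is not always added vasopressor. Treatment of hypotension is unchanged.

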5.5.6 Rescue medication

The investigator may prescribe any medications and/or supportive care during the study based on clinical needs. Use of rescue medication and/or supportive care must be recorded on the Concomitant medications/Significant non-drug therapies in the eCRF.

5.5.7 Concomitant treatment

The investigator may prescribe any additional medications and/or supportive care during the study as dictated by the patient's condition, except for those listed in [Section 5.5.8](#) Prohibited Treatment. Administration of standard treatment should in no instance be delayed or withheld due to patient's participation in the study. Standard treatment includes, but is not limited to, administration of the major classes of iv, enteral or topical medications, transfusion of blood products mechanical ventilation, diagnostic examinations, positioning, endotracheal and oropharyngeal suctioning, physio- or ergotherapy, as needed. Any medication or non-medical therapy added, discontinued or modified during the study should be recorded on the eCRF. The investigator should instruct the patient and/or legal guardian to notify the investigator or associated study personnel about any new medications he/she takes after the patient was enrolled into the study.

All medications, procedures and significant non-drug therapies (including physical therapy and blood transfusions) administered after the patient was enrolled into the study must be recorded.

5.5.8 Prohibited Treatment

Subjects will not be enrolled in the study if concomitant therapy for AHF includes current or planned treatment with levosimendan or nesiritide during the study. This is because of the potential for the administration of these drugs to interfere with the study endpoints.

Patients on ECMO, VAD or RRT will not be enrolled because of the potential interference of the extracorporeal circuit with the PK profile of serelaxin.

After enrollment, the investigator may prescribe any additional medication as dictated by the patient's condition. Administration of standard treatment should never be delayed or withheld due to patient's participation in the study. The investigator should exercise caution when up-titrating or adding concomitant standard therapies that might decrease BP during study drug infusion. Changes to any co-medication or non-medical treatment during the hospitalization should be recorded on the eCRF.

5.5.9 Discontinuation of study treatment

Discontinuation of study treatment: The investigator should discontinue the study drug infusion for a patient if, on balance, he/she believes that continuation would be detrimental to the patient's well-being.

In particular, the study drug administration must be discontinued under the following circumstances:

- Withdrawal of informed consent-or assent
- Intolerable adverse events, thought to be related to study drug, which persist
- If the SBP falls <5th percentile for the age of the patient ([AHA PALS guidelines 2010, Kleinman 2010](#), see [Appendix 4](#)) and is considered a confirmed SBPDE, then follow the instructions outlined in [Section 5.5.5](#).
- Use of prohibited treatment as per [Section 5.5.8](#)
- Pregnancy
- Surgical intervention during the study drug infusion
- A patient should not remain in the ICU/CCU or a continuously monitored step-down Unit for the sole purpose of study drug infusion. The decision to discharge a patient from the ICU/CCU or a continuously monitored step-down unit should be made per SOC. If the serelaxin infusion is still ongoing at the time of transfer out of the ICU/CCU or a continuously monitored step-down unit, the study drug infusion is to be discontinued.

Patients who discontinue study treatment should NOT be considered withdrawn from the study. They should be followed per the visit/assessment schedule illustrated in [Table 6-1](#) until the study is complete. If they fail to return for these assessments for unknown reasons, every effort should be made to contact them as specified in [Section 5.5.11](#).

Patient withdrawal: Patients/legal guardians may voluntarily withdraw consent or assent for any reason at any time.

Withdrawal of consent or assent occurs only when a patient/legal guardian does not want to participate in the study anymore and, does not want any further visits or assessments and, does not want any further study related contacts and does not allow analysis of already obtained biologic material.

If a patient/legal guardian withdraws consent or assent, the investigator must make every effort to determine the primary reason for this decision and record this information. Study treatment must be discontinued and no further assessments conducted. All biological material that has not been analyzed at the time of withdrawal must not be used. Further attempts to contact the patient/legal guardian or patient are not allowed unless safety findings require communicating or follow-up.

Patients/legal guardians can refuse to participate in specific aspects of the study and/or take study medication at any time without withdrawing consent. Investigators should make every effort to accommodate the needs of the patients to make it possible for them to continue to participate in the remaining aspects of the study.

Lost to follow-up: For patients whose status is unclear because they fail to appear for study visits without stating an intention to withdraw, the investigator should show "due diligence" by contacting the patient, legal guardians, family or family physician as agreed in the informed consent and by documenting in the source documents steps taken to contact the patient, e.g. dates of telephone calls, registered letters, etc. A patient should not be considered lost to follow-up until his/her scheduled end of study visit would have occurred.

The investigator must also contact the IRT (Interactive Response Technology) to register the patient's discontinuation from the study drug.

